8.2 Supportive Care

- 8.2.1 All supportive measures consistent with optimal patient care will be given throughout the study.

9 STUDY CALENDAR

1 cycle = 28 days¹¹

Examination	Screening ¹	Neo-adjuvant C1	EBRT	C2 ⁷	C3	C4	C5	C6	End of Treatment ¹⁷	Follow-up ⁸
Informed consent	X									
Medical history	X									
Eligibility criteria	X									
Vital signs	X	X		X	X	X	X	X	X	
Physical examination ¹⁸	X	X		X	X	X	X	X	X	X
Karnofsky Performance Status or ECOG Equivalent (Appendix 17.5) ¹⁸	X	X		X	X	X	X	X	X	
Concomitant Medications ¹⁸	X	X	X	X	X	X	X	X	X	X
Adverse Events ¹⁴		X	X	X	X	X	X	X	X	X
Hematology ^{2, 13}	X	X ¹³		X ¹³	X					
Chemistry ^{3, 13}	X	X ¹³		X ¹³	X					
ECG ⁵	X									
CT or MRI ⁴	X								X	
Radium-223 ¹⁶		X		X	X	X	X	X		
EBRT			X							
PSA and Testosterone ^{9, 13}	X	X	X ⁹	X	X	X	X	X	X	X
Bone scans ⁶	X			X ¹²	X ¹²	X	X ¹²	X ¹²	X	X
QOL questionnaires	X		X ¹⁵			X			X	X
Myriad CCP ¹⁰	X									
Myriad HRD ¹⁰	X									

- 1 ALL Pre-study/Screening procedures should be completed within 4 weeks of study enrollment - with the exception of laboratory tests which need to be completed within 2 weeks prior to study enrollment, and imaging assessments which must be completed within 90 days of enrollment. Consent may be signed \leq 45 days prior to cycle one day one.
- 2 Hematology includes CBC with differential and platelets.
- 3 Chemistry includes Albumin, Alkaline Phosphatase, Aspartate Aminotransferase, Alanine Aminotransferase, Total Bilirubin, Calcium, Carbon Dioxide, Creatinine, Chloride, Glucose, Potassium, Protein, Sodium, Urea Nitrogen. 4 CT-based scans (either Fluciclovine PET/CT or diagnostic CT) or MRI that includes the chest, abdomen and pelvis. A similar imaging modality (MRI or CT-based) used at screening is preferred, but not required at follow up evaluation. Diagnostic CT at follow-up is sufficient if PET/CT was used at screening. Disease assessment to be conducted by PCWG2 and RECIST 1.1 section 10.1.1.
- 5 ECG will be done only if medically indicated.
- 6 Bone scans should be obtained between cycle 3 and 4 of the study dependent on any dose delays that may extend cycle time. Bone scans should be performed 2-4 weeks after the final Radium-223 dose. Bone scans will also be performed at any sign of progression as defined in section 10.
- 7 Cycle 2 may be delivered concurrently with external beam radiation to the primary site. Therefore, cycle 2 will NOT be delayed to allow completion of the external beam radiation.
- 8 Follow-up visits will occur every 3 months (+90/-30 days) for an approximate duration of two years from the time patients are enrolled on the study.
- 9 PSA and Testosterone within 24 hours prior to or after starting external beam radiation.
- 10 Correlative studies are OPTIONAL; refer to section 14.1 for archival tissue instruction
- 11 Cycles should occur at least 28 days after the previous cycle and no more than 42 days after the previous cycle (0 to +14 days).
- 12 Bone scans are optional at the time points indicated by this superscript and will be performed if there is clinical suspicion of progression that falls outside the objective criteria of progression for this study.
- 13 All post-screening laboratory tests should be drawn approximately 7 days, but no fewer than 3 business days, before radium dosing. Laboratory tests for CBC differential platelets must have results available prior to radium ordering. Laboratory safety assessments MUST be performed and resulted prior to radium dosing.
- 14 The collection of all adverse events will begin after the first dose of study treatment and end 30 days after the last dose of study treatment. The collection of treatment related adverse events will continue until the last study visit (or until new cancer treatment is initiated, if sooner).
- 15 QOL Questionnaires should be completed on the final day of EBRT \pm 7days.
- 16 If a patient meets biochemical progression, the patient may continue to receive treatment, at the Investigator's discretion, until a validated PSA test has confirmed biochemical progression.
- 17 End of treatment visit will occur 28 days (\pm 7 days) after last treatment is administered.
- 18 Physical exam, KPS or ECOG equivalent, and concomitant medications do not need to be repeated if they have been performed less than 7 days prior.

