1.1 Primary Objectives and Endpoint

1.1.1 Determine if 20% of ADT naïve men treated with concurrent EBRT and Radium-223 will not require ADT for progression by 15 months.
Endpoint: Determine the time from start of study therapy to start of ADT.

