10.1 Primary Endpoint – 15 month Hormone Free Survival

The primary objective is to determine the hormone-therapy-free survival time for men treated with sequential EBRT and Radium-223 and determine whether it is a 20% risk reduction over the institutional comparator of 100% use of systemic therapy by 15 months. The primary outcome is 15 months hormone-free survival. Patients will remain on study treatment for the duration defined by the calendar or for disease progression. Patients will be followed up to determine the start of ADT which will be used to measure the primary end point.

For the purposes of this study, progression will be measured after the completion of EBRT and the delivery of Cycle 2 of Radium-223 and defined as either:

Biochemical Progression:

- For those subjects whose PSA is greater than 20ng/ml at baseline who do not have any PSA decrease after starting therapy: biochemical progression will be defined as a 10% rise over the baseline.

- For those subjects whose PSA is greater than 20ng/ml at baseline, who demonstrate decrease in PSA after study treatment: if the PSA nadir remains > 20ng/ml, biochemical progression will be defined as a PSA rise greater than 10% of the PSA nadir. If the PSA nadir is < 20ng/ml, biochemical progression will be defined as a PSA rise greater than 10% of the PSA nadir.

-For those subjects whose PSA is less than 20ng/ml at baseline: biochemical progression will be defined as PSA >20ng/ml and 10%.

*Any PSA test that would meet a failure definition has to be validated through Huntsman Cancer Institute or a Veterans Affairs Hospital with a repeat PSA test no sooner than 5 days and no later than 14 days from the initial notification of the result demonstrating progression.

OR

Radiographic progression: Any new, progressing, or reappearing lesion on Bone Scan, CT/Scan, or MRI compared to the same scan performed previously. Radiographic Progression will be determined by Prostate Cancer Clinical Trials Working Group (PCWG2) and RECIST 1.1 as described below (section 10.1.1).

* Of note: For a patient to meet radiographic progression criterion for appearance of new bone lesion only, the patient must demonstrate appearance of new bone disease, as confirmed by the treating radiation oncologist, and also meet the biochemical progression definition set out above.

OR

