11 STATISTICAL CONSIDERATIONS

The primary objective is to determine the hormone-therapy-free survival time for men treated with concurrent EBRT and Radium-223 and determine whether 20% of subjects do not meet the progression endpoint and require ADT at 15 months. The primary outcome is 15 months hormone- (or other systemic) therapy-free survival. The null hypothesis is that 99% of subjects will start systemic therapy within 15 months. The alternative hypothesis is that 80% of subjects will start systemic therapy within 15 months. With 20 evaluable subjects there will be 93% power for this alternative hypothesis using an exact binomial test at the one-sided 0.05 significance level. The null hypothesis will be rejected if 2 or more out of 20 subjects are not placed on systemic therapy within one year.

One of the secondary endpoints is to determine the hormone-therapy-free survival time for men treated with concurrent EBRT and Radium-223 and determine whether it is a 30% risk reduction over the SWOG intermittent ADT historic cohort. This secondary hypothesis will be tested only if the primary null hypothesis is rejected. The outcome for

this secondary hypothesis is 15 month hormone- (or other systemic) therapy-free survival. In 2012 a SWOG cooperative group trial reported that 78% of subjects on intermittent androgen therapy had resumed ADT within 15 months, and this proportion will be used as a null hypothesis. With 20 evaluable subjects, and a null hypothesis that 78% or more of patients will start systemic therapy within 15 months there will be 80% power to detect an alternative hypothesis that 48% or fewer will start systemic therapy within 15 month using an exact binomial test at one-sided alpha =0.05 significance level.

Additional, secondary endpoints are time to first skeletal related event (SRE), overall survival, PSA doubling time, overall survival and toxicities. All secondary endpoints will be evaluated descriptively. Time to first SRE, OS, and PSA doubling time will be analyzed via Kaplan-Meier product limit methods and associated 95% confidence intervals. Toxicities will be tabulated using CTAE version 4.0. The number and proportion of subjects with toxicities will be reported.

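### No PSA has to be drawn early enough to be confirmed before the 15-month landmark, and the +90/-30-day visit window allows about six months between scheduled PSAs

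*Combined protocol and SAP*

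**What the plan says.** Section 1.1 sets the aim as showing that 20% of men "will not require ADT for progression by 15 months", with the endpoint "Determine the time from start of study therapy to start of ADT". Section 10.1 adds: "Patients will be followed up to determine the start of ADT which will be used to measure the primary end point". Section 11 widens the outcome to other systemic therapy. It states "The null hypothesis is that 99% of subjects will start systemic therapy within 15 months" and "The alternative hypothesis is that 80% of subjects will start systemic therapy within 15 months", and rejects the null if 2 or more of 20 men are free of systemic therapy.

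On assessment timing, the study calendar (Section 9, footnote 8) says "Follow-up visits will occur every 3 months (+90/-30 days) for an approximate duration of two years". The two years run from enrolment. The footnote does not say whether the three-month interval runs from enrolment, from end of treatment or from the previous visit. In follow-up, PSA is scheduled only at these visits.

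A PSA that meets the failure definition must be validated "with a repeat PSA test no sooner than 5 days and no later than 14 days from the initial notification of the result" (Section 10.1). In the same section, radiographic progression that rests only on new bone lesions counts only if the PSA definition is also met.

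**The concern.** The late allowance is as long as the visit interval, and nothing requires an assessment to be finished before the landmark on which the primary decision rests. The endpoint is the date ADT starts, but ADT is meant to follow progression. In a man without symptoms, progression is found mainly through PSA. If his PSA is first drawn at about month 15, confirmation falls after the landmark, and he counts as ADT-free although he progressed earlier.

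Late detection can only postpone ADT, so the error favours the treatment. There is no concurrent control to share it. The decision turns on two men, so even one or two such cases matter.

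**Working it through.** **Inputs.** From Section 11: 20 evaluable men, cut-off 2, null 1% free, alternative 20% free, stated power 93%, one-sided 0.05. From Section 9, footnote 8: a 3-month interval, +90/-30 days. From Section 10.1: a repeat PSA 5 to 14 days after notification. From Section 1.1: the clock starts with study therapy.

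**Assumptions.** A month is 30.4375 days. Visits are counted from enrolment, and enrolment coincides with the first cycle (Section 7.2). Notification is on the day of the draw. The rejection sentence in Section 11 says one year where the hypotheses say 15 months. I use 15 months, and the two must be reconciled separately.

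**1. The plan's own figure.** P(X ≥ 2) = 1 - (1-p)^20 - 20p(1-p)^19.
- p = 0.20 gives 0.931, so the stated 93% power is reproduced.
- p = 0.01 gives 0.017, a type I error of 1.7%.

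**2. Calendar.**
- Landmark: 15 × 30.4375 = day 456.6.
- Month-12 visit at +90 days: 365.25 + 90 = day 455.3. Confirmation follows on days 460.3 to 469.3.
- Punctual month-15 visit: day 456.6. Confirmation follows on days 461.6 to 470.6.
- Permitted range for the month-15 visit: days 426.6 to 546.6.
- Gap from a punctual month-9 visit (day 273.9) to a late month-12 visit: 455.3 - 273.9 = 181 days, about 6.0 months. If the month-9 visit is 30 days early, the gap is 211 days (6.9 months).
- Counting from the previous visit: 91.3 + 90 = 181 days, again about 6 months.

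**3. Sensitivity of the decision rule.**
- One man carried past the landmark, 19 others at 1%: 1 - 0.99^19 = 17.4% chance of rejection.
- Two such men meet the rule on their own.
- By apparent ADT-free share under the null, type I error is 3.6% at a share of 1.5%, 6.0% at 2%, 12.0% at 3% and 26.4% at 5%. It passes 5% at a share of about 1.8%.

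**4. Illustration.** Assume exponential times to progression with 99% by month 15, and therapy starting as soon as progression is confirmed. Then λ = -ln(0.01)/15 = 0.307 per month and S(t) = exp(-λt).
- Perfectly punctual visits: everyone who progresses after month 12 is found at month 15 and confirmed too late. The free share is S(12) = 0.0251, so type I error is 8.9% (about 8.8% by simulation).
- Visits at months 6, 9, 12, 15 and so on, the first fixed and the others uniform in their windows, with 14-day confirmation: about 7.3% with +90/-30 days and 6.9% with ±30 days. A repeat simulation gave 7.2% and 7.1%, so the two windows are practically the same. Both fall below the punctual figure because some visits land shortly before the landmark.

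**5. PSA timed for the landmark.** The latest useful draw is 456.6 - 14 = day 442.6. The existing -30-day allowance opens at day 426.6. Only men who progress after the draw are missed.
- Day 442 (14.52 months): S = 0.0116, error 2.2%.
- Day 440 (14.46 months): S = 0.0118, error 2.3%.
- Day 427 (14.03 months): S = 0.0135, error 2.9%.

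**The case against.** The strongest objection is that the window is not the cause. A reader might infer that footnote 8 itself lifts type I error from 1.7% to 5.2% or 8.9%, because under the exponential model a 2- or 3-month delay for every man leaves S(13) = 1.85% or S(12) = 2.5% apparently free. The documents do not support that. They show no systematic delay of that size, and the same model gives 8.9% with no visit window at all. Nor would ±30 days solve the problem, since a month-15 visit could still fall on day 486.6 (month 16). This objection stands in full.

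The model is also weak. It implies a median of ln 2/0.307 = 2.3 months, with 84% of events before month 6, when PSA is mostly drawn at treatment cycles and footnote 8 does not apply. The 99% null and the institutional 100% are shares started on therapy, so they may already contain a detection lag. Section 2 describes immediate ADT as standard care, so comparator starts need not follow PSA detection. This stands too: the error rates are illustrations, not estimates.

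The protocol names no month-12 or month-15 visit; that grid is my reading. A gap of about six months follows equally if visits are counted from the previous one.

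Finally, the endpoint is the actual ADT date. Symptoms, a skeletal event, a bone scan prompted by suspected progression or an unscheduled PSA could all bring ADT forward. That limits how often the problem arises, but none of these guarantees a PSA before month 15 in a man without symptoms.

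**Conclusion.** The gap is real. The protocol lets about six months pass without a scheduled PSA and requires no assessment whose confirmation is complete by 15 months. A PSA first drawn at about month 15 is confirmed too late, whether it comes from a punctual visit or from a month-12 visit at the end of its window. The resulting error favours the treatment, under a rule that two men can satisfy.

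Its frequency cannot be estimated from the documents. On the exponential assumption, the main driver is three-monthly assessment plus confirmation at the landmark (about 8.9% with punctual visits). The wide window does not add to this on an enrolment grid (about 7%). The calendar result assumes that enrolment and first treatment coincide. Section 12 allows up to 21 working days between registration and treatment; if visits were counted from registration, they would fall earlier on the therapy clock. That is a further reason to state the anchor.

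**What to change.** - State in footnote 8 what the three months are counted from, preferably the start of study therapy, to match the endpoint.
- Shorten the late window for visits before the landmark so that neighbouring visits cannot merge.
- Require the already scheduled PSA near month 15 to be drawn between about day 427 and day 442 from start of study therapy, so that the repeat test is complete by 15 months. The 14 days run from notification, so day 442 leaves no room for laboratory turnaround. An earlier draw leaves room but misses slightly more late progression (2.9% against 2.2% in the illustration).
- Add a sensitivity analysis that dates the event at the first PSA or scan later confirmed as progression. It is still limited by visit timing and does not replace the ADT-start endpoint. It is useful because the protocol sets no interval between confirmed progression and ADT start, which visit timing alone cannot address.
- Present any type I error figure for detection delay as illustrative, with its assumptions.

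The cost is tighter scheduling of one or two visits and a few more window deviations. No new procedure is needed, so this is a cheap improvement.

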7 TREATMENT GUIDELINE

7.1 External Beam Radiation Administration Schedule

7.1.1 All external beam radiations oligometastatic sites will commence after cycle one of Radium-223 but prior to cycle two of Radium-223.

7.1.1.1 All lesions seen on bone scan and corroborated by the validating scans will be treated. If there are additional suspicious bone lesions seen on Bone scan, CT, MRI, PET/CT, or treatment-planning simulation scans, but not corroborated by a second scan, they can be targeted at the treating physician's discretion as long as no more than 5 lesions total are targeted with external beam radiation.

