7.1.2 External Beam radiation for Oligometastasis

7.1.2.1 Dose Specification

All subjects will receive Stereotactic body or hypofractionated radiation to sites of bone disease seen on imaging studies using any one of the isoequivalent radiation regimens (based on the linear quadratic model with EQD2=60gy and an alpha/beta ration for prostate cancer= 2). EQD2 (equivalent radiobiological dose if converted to 2Gy daily fractions) is being utilized to allow the radiation oncologist the flexibility to give an ablative dose to tumor but allow for differing regimens to spare critical normal tissues depending on tumor location.

Any of the following regimens are considered ablative, acceptable, and are biologically equivalent to 60Gy EQD2:

- Single fraction: 16 Gy total at 16 Gy per fraction (SBRT)
- Three fractions: 24 Gy total at 8 Gy per fraction (SBRT)
- Five fractions: 30 Gy total at 6 Gy per fraction (SBRT). When using five fractions, can reduce to 25 Gy total at 5 Gy per fraction (SBRT) or to a minimum of 20 Gy total at 4 Gy per fraction (SBRT), per treating investigator.
- Six fractions: 32.4 Gy total at 5.4Gy per fraction (Hypofractionated)

If any of the fractions need to be further reduced, this can be done in consultation with the medical monitor.

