17 APPENDIX

17.1 PROMIS-29 Questionnaire

RROPE

PROMIS-29 Questionnaire

Patient Study ID: 102312-01-_____

Patient Initials: _____

Date of Completion: _____ / _____ / _____

PROMIS-29 Profile v1.0

Please respond to each question or statement by marking one box per row.

Physical Function		Without any difficulty	With a little difficulty	With some difficulty	With much difficulty	Unable to do
		1	Are you able to do chores such as vacuuming or yard work?			
2	Are you able to go up and down stairs at a normal pace?					
3	Are you able to go for a walk of at least 15 minutes?					
4	Are you able to run errands and shop?					
Anxiety		Never	Rarely	Sometimes	Often	Always
5	In the past 7 days... I felt fearful					
6	I found it hard to focus on anything other than my anxiety					
7	My worries overwhelmed me					
8	I felt uneasy					
Depression		Never	Rarely	Sometimes	Often	Always
9	In the past 7 days... I felt worthless					
10	I felt helpless					
11	I felt depressed					

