All of the Time	Most of the Time	A Good Bit of the Time	Some of the Time	A Little of the Time	None of the Time
--------------------------	---------------------------	------------------------------------	---------------------------	----------------------------------	---------------------------

a. Have you felt calm and peaceful? 1 2 3 4 5 6 19/
b. Did you have a lot of energy? 1 2 3 4 5 6 20/
c. Have you felt downhearted and blue? 1 2 3 4 5 6 21/

7. During the past 4 weeks, how much of the time has your physical health or emotional
problems interfered with your social activities (like visiting with friends, relatives, etc.)?

22/

All of the time 1
Most of the time 2
Some of the time 3 (Circle one number)
A little of the time 4
None of the time 5

URINARY FUNCTION

This section is about your urinary habits. Please consider **ONLY THE LAST 4 WEEKS**.

8. Over the past 4 weeks, how often have you leaked urine?

More than once a day.....	1
About once a day.....	2
More than once a week.....	3
About once a week.....	4
Rarely or never.....	5

23/

9. Over the past 4 weeks, how often have you urinated blood?

More than once a day.....	1
About once a day.....	2
More than once a week.....	3
About once a week.....	4
Rarely or never.....	5

24/

10. Over the past 4 weeks, how often have you had pain or burning with urination?

More than once a day.....	1
About once a day.....	2
More than once a week.....	3
About once a week.....	4
Rarely or never.....	5

25/

11. Which of the following best describes your urinary control during the last 4 weeks?

No urinary control whatsoever.....	1
Frequent dribbling.....	2
Occasional dribbling.....	3
Total control.....	4

26/

12. How many pads or adult diapers per day did you usually use to control leakage during the last 4 weeks?

None	0
1 pad per day.....	1
2 pads per day.....	2
3 or more pads per day.....	3

(Circle one number)

27/

13. How big a problem, if any, has each of the following been for you during the last 4 weeks?

(Circle one number on each line)

	No Problem	Very Small Problem	Small Problem	Moderate Problem	Big Problem	
a. Dripping or leaking urine	0	1	2	3	4	28/
b. Pain or burning on urination.....	0	1	2	3	4	29/
c. Bleeding with urination.....	0	1	2	3	4	30/
d. Weak urine stream or incomplete emptying.....	0	1	2	3	4	31/
e. Waking up to urinate.....	0	1	2	3	4	32/
f. Need to urinate frequently during the day	0	1	2	3	4	33/

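### The ± 7-day window for the EBRT quality-of-life questionnaire lets it be completed before any EBRT when the course spans fewer than 7 days

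*Combined protocol and SAP*

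**What the plan says.** Section 9 (Study Calendar) schedules the quality-of-life questionnaires at screening, EBRT, Cycle 4, end of treatment and follow-up. None is scheduled at Cycle 2 or Cycle 3. Footnote 15 governs the EBRT assessment: "QOL Questionnaires should be completed on the final day of EBRT \pm 7days". No rule says that it must come after a fraction has been given.

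The length of EBRT is described in two places:

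- Section 7.1.2.1 lists acceptable regimens per site, from "Single fraction: 16 Gy total at 16 Gy per fraction (SBRT") to "Six fractions: 32.4 Gy total at 5.4Gy per fraction (Hypofractionated"). Three and five fractions are also listed. Spacing between fractions is not given.
- Section 7.4 expects the EBRT phase to take 2 to 6 weeks.

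Section 7.1.1 says that EBRT to the metastatic sites "will commence after cycle one of Radium-223 but prior to cycle two of Radium-223". Section 7.1.1.1 caps EBRT at five lesions, but the plan does not say whether lesions are treated together or in turn.

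The instruments look back over different periods. EPIC (Appendix 17.2) uses four weeks, for example "Over the past 4 weeks, how often have you leaked urine". PROMIS-29 (Appendix 17.1) mostly uses one week, for example "In the past 7 days... I felt fearful"; its physical-function items state no recall period.

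Quality of life is secondary objective 1.2.2. Section 11 plans medians, ranges and quartiles for each domain, plus exploratory logrank tests.

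**The concern.** The window is anchored on the last day of EBRT but extends 7 days to either side. If the whole course fits within a few days, the early side of the window lies before the first fraction. A score taken then carries no information about EBRT, yet it complies with the calendar and would be summarised with the other EBRT scores. Even after a short course, a four-week recall ending near the last fraction is mostly filled by earlier weeks.

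With 20 men and a summary by medians and quartiles, one EBRT column could combine questionnaires that saw no EBRT with questionnaires whose whole recall period lay within it. Any early effect of EBRT on urinary, bowel or pain scores, in either direction, would be diluted by an amount that varies from man to man for scheduling reasons only.

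**Working it through.** The plan gives no figure of its own on this point, so the check is calendar arithmetic.

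**Inputs**

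- Questionnaire day relative to the last EBRT day: *t* from -7 to +7 (footnote 15).
- Recall length: *R* = 28 days for EPIC, 7 days for PROMIS-29 (Appendices 17.2 and 17.1).
- Days from first to last EBRT day: *D*. A single fraction gives *D* = 0 (Section 7.1.2.1). An EBRT phase of 2, 4 or 6 weeks gives *D* = 14, 28 or 42 (from the range in Section 7.4). Values for 3, 5 and 6 fractions are assumptions: *D* = 2 to 6 for three or five fractions within one week, and *D* = 7 for six daily fractions across a weekend.

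**Can the questionnaire precede all EBRT?** The earliest permitted day is *D* - 7 days after the first fraction. It falls before the first fraction when *D* < 7.

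**Share of recall on or after the start of EBRT**

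Share = max(0, min(*R*, *D* + *t*)) / *R*. Counting both end days replaces *D* + *t* with *D* + *t* + 1.

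Single fraction, EPIC:
- *t* = -7: 0/28 = 0%
- *t* = 0: 0/28 = 0% (1/28 = 4% counting both end days)
- *t* = +7: 7/28 = 25% (8/28 = 29%)

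Single fraction, PROMIS-29:
- *t* = -7: 0/7 = 0%
- *t* = 0: 0/7 = 0% (1/7 = 14%)
- *t* = +7: 7/7 = 100%

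All cases, in elapsed days:

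| EBRT span | Before any EBRT possible? | EPIC at -7 / 0 / +7 | PROMIS-29 at -7 / 0 / +7 |
|---|---|---|---|
| Single fraction (*D* = 0) | Yes | 0 / 0 / 25% | 0 / 0 / 100% |
| Within one week (*D* = 2 to 6, assumed) | Yes | 0 / 7-21% / 32-46% | 0 / 29-86% / 100% |
| Six fractions (*D* = 7, assumed) | No | 0 / 25% / 50% | 0 / 100% / 100% |
| 2 weeks (*D* = 14) | No | 25% / 50% / 75% | 100% throughout |
| 4 weeks (*D* = 28) | No | 75% / 100% / 100% | 100% throughout |
| 6 weeks (*D* = 42) | No | 100% throughout | 100% throughout |

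**What the next questionnaire adds.** Cycles are at least 28 days apart (footnote 11), so Cycle 4 is at least 2 × 28 = 56 days after Cycle 2. If the Cycle 4 questionnaire is completed on the dosing day, its EPIC recall begins no earlier than 56 - 28 = 28 days after Cycle 2. Section 7.2 puts Cycle 2 after radiotherapy is complete. On that reading at least 28 days after EBRT lie outside the EPIC recall if the EBRT questionnaire is done on the last EBRT day, and at least 28 - 7 = 21 days if it is done at day +7.

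**The case against.** The strongest reply is that Section 7.4 expects EBRT to take 2 to 6 weeks and that up to five lesions may be treated. On that footing the questionnaire cannot precede EBRT, and a substantial part of the EPIC recall falls within it. This stands for men treated over that length of time. It does not remove the gap, because Section 7.4 states an expectation rather than a minimum and Section 7.1.2.1 accepts a one-day course.

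A second reply is that little depends on this score. Quality of life is a descriptive secondary endpoint, no planned analysis isolates the EBRT time point, and later questionnaires follow EBRT. Adverse events are also graded at EBRT, Cycle 2, Cycle 3 and later visits and attributed to radium or EBRT (Sections 9 and 15.4.1), so acute bowel or urinary toxicity is recorded, though not as a patient-reported score. All of this stands, and it limits the weight of the point.

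Two stronger readings are tempting. A reader might infer that the EBRT score will resemble baseline whatever EBRT does. The documents do not support that: at day +7 even a single-fraction course has a PROMIS-29 recall wholly after EBRT and 25 to 29% of the EPIC recall on or after it. A reader might also infer that no questionnaire covers the weeks just after EBRT. A questionnaire at day +7 covers the first week on both instruments. What is supported is a gap between that questionnaire and the start of the Cycle 4 recall.

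**Conclusion.** The point holds for short courses. As written, footnote 15 permits an EBRT questionnaire before any EBRT whenever first and last EBRT days are fewer than 7 days apart. A single fraction always meets that condition. Three or five fractions within one week also meet it, on an assumed spacing. For a single fraction, at least 71 to 75% of the EPIC recall precedes EBRT wherever in the window the questionnaire falls.

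The point does not extend to every course. With an EBRT phase of 2 weeks or more, collection before EBRT is impossible and the EPIC share ranges from 25% to 100%. How many of the 20 men fall on each side cannot be worked out, since neither fraction spacing nor the sequencing of lesions is given. Sections 7.1.2.1 and 7.4 imply different EBRT lengths and need to be reconciled. The consequence is a blurred descriptive time point for objective 1.2.2; the primary analysis is unaffected.

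**What to change.** In footnote 15, replace the ± 7-day window with *0 to +7 days after the final fraction of EBRT to the metastatic sites*, preferably near day +7. The score then never precedes EBRT, and near day +7 the PROMIS-29 recall covers the week after it. Naming the metastatic sites matters because footnote 7 allows EBRT to the primary site to run alongside Cycle 2. Reconcile Sections 7.1.2.1 and 7.4 on EBRT length in the same amendment.

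The cost is one footnote and a scheduling window of 8 days instead of 15, with no added visit or questionnaire. For single-fraction courses at least 71% of the EPIC recall still precedes EBRT, and this should be stated when the score is interpreted. The gap before the Cycle 4 recall also remains.

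Moving the questionnaire to the Cycle 2 visit is not recommended. The 7-day PROMIS-29 recall could then miss the first week after EBRT. A late EBRT start would gain little: EBRT on day 27 with Cycle 2 on day 28 gives an EPIC share of 1/28 = 4%. Footnote 7 also means that Cycle 2 need not follow the last fraction to the primary site.
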